#### 3.2 Secondary Objectives

The secondary outcomes are the comparison between the changes in the mean of clinical, imaging and biomic outcomes in various subsets between the two groups. The secondary outcome instruments are:

MRI scan of the brain (Day 2 and Day 9), to determine whether the blood brain barrier integrity can be measured in ALS by Magnetic Resonance Imaging, and whether 3K3A-APC is able to repair it. In addition novel methods of measuring diffusion kurtosis, a marker of neuronal injury will be used.

Extensive biomic measurements of serum, plasma, urine and CSF will be performed. These will include a novel method to determine whether monocyte activation in the peripheral blood can act as a surrogate marker of microglial activation state in ALS. In addition multiplex cytokine and chemokine assays will determine the biological impact of the therapy. Neurofilament, soluble CD14 and kynurenine (and other) measurements will be used to look at acute changes as a result of 3K3A-APC. These methods will determine whether 3K3A-APC therapy is able to attenuate the altered cytokine and metabolic profiles in ALS.

It is highly unlikely that such an acute dosing regimen will identify neurological changes in the subjects, but accurate clinical and biophysical measurements will be performed to detect any such change should they occur.

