Primary Outcome	
The primary study outcomes are:
 
To ensure the safety of patients with ALS administered a range of doses of 3K3A-APC according to a fixed dose regimen of five doses of 15mg or 30mg doses given 12 hours apart.
 
This study also aims to determine whether a novel therapy, 3K3A-APC, is able to attenuate microglial activation in the motor cortex of patients with amyotrophic lateral sclerosis utilizing serial [F]FEMPA PET imaging (Day 2 and Day 9). In addition, the study design will include two (2) dose cohorts with eight patients in each cohort, with the initial cohort to receive 15mg and the subsequent cohort to receive 30mg, to determine the dose of 3K3A-APC that is shown to be most effective in reducing microglial activation. If microglial activation can be attenuated in ALS, then the progression of ALS might be slowed.

Secondary Outcomes	
The secondary outcomes are:
 
 
• Comparison between the changes in the mean of clinical, imaging and biomic outcomes in various subsets between the two dose cohorts.
 
• The secondary outcome instruments to be employed are: 
 
• MRI scan of the brain (Day 2 and Day 9), to determine whether the blood brain barrier integrity can be measured in ALS by Magnetic Resonance Imaging, and whether 3K3A-APC is able to repair it.
 
• Biomic measurements of serum, plasma, urine and CSF. This includes a novel method to determine whether monocyte activation in the peripheral blood can act as a surrogate marker of microglial activation state in ALS.
 
• These methods will determine whether 3K3A-APC therapy is able to attenuate the altered cytokine and metabolic profiles in ALS.
 
 
 

Safety Assessments	
Incidence of adverse events, proportion of withdrawals due to adverse events, vital signs and clinical laboratory assessment changes from baseline. Clinical safety laboratory data (haematology, biochemistry, and urine chemistry) will be summarised at each protocol scheduled time point, by

	dose cohort, and overall. Observed values, change from baseline will be presented.

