## 4. Study Outcome

The mean rates of change and the variability around the mean of clinical, imaging and biomic outcomes in the two ALS patient cohorts will be determined over the study period. The results will inform potential future studies of the therapeutic potential of 3K3A-APC in ALS patients, and guide dosing for chronic studies.

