## 15. Statistical Analysis

### 15.1 Demographic and Baseline Characteristics

Descriptive analyses will be reported for this study. Continuous parameters, will be summarised as the number of observations, mean, median, standard deviation, minimum, maximum, and if appropriate two-sided 95% CI's. Categorical parameters will be summarised as frequencies, percentages, and exact Clopper-Pearson two-sided 95% CI's. Data will be summarised by dose cohort, and overall.

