## 15.2 Primary efficacy variables

Adverse events will be coded using the most recent version of the Medical Dictionary for Regulatory Activities (MedDRA) coding system to give a System Organ Class (SOC) and Preferred Term (PT) for each adverse event (AE).

Treatment emergent AEs will be defined as AEs with an onset date on or after the date of administration of study drug. If the onset date is missing, the AE will be considered to be treatment emergent. Only treatment-emergent AEs will be summarized. All reported AEs will be listed. The number of AEs, and the number and percentage of patients reporting at least one AE will be summarized by PT nested within SOC for required AE types. AE data will be summarized by dose cohort, and overall.

Microglial activation as measured by [F] FEMPA will be summarised at each time point for each dose cohort and overall as observed value, change from baseline, and % change from baseline. Microglial activation will be summarised with number of observations, mean, median, standard deviation, minimum, maximum, and two-sided 95% CI's.

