## 15.3 Secondary efficacy variables:

The secondary efficacy variables of MRI scan of the brain, and biomic measurements of serum, plasma, urine and CSF will be summarized over time for each dose cohort, and overall as for the primary efficacy variables.

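### The plan asks whether blood monocyte activation can stand in for microglial activation, but the planned output summarises the two markers only separately and so cannot answer that

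*Combined protocol and SAP*

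**What the plan says.** Section 3.2 (Secondary Objectives) states that the biomic work includes "a novel method to determine whether monocyte activation in the peripheral blood can act as a surrogate marker of microglial activation state in ALS". The Secondary Outcomes row of the synopsis likewise asks whether "monocyte activation in the peripheral blood can act as a surrogate marker of microglial activation state in ALS". Section 1 says that monocyte activation is measured by flow cytometry of peripheral blood. Section 3.1 says that microglial activation is measured in the motor cortex by [18F]FEMPA PET.

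The analysis text is in Section 15, and the synopsis gives the same methods:

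- Section 15.1: "Descriptive analyses will be reported for this study".
- Section 15.2: the PET measure is "summarised at each time point for each dose cohort and overall as observed value, change from baseline, and % change from baseline", with the usual summary statistics and two-sided 95% CIs.
- Section 15.3: "biomic measurements of serum, plasma, urine and CSF will be summarized over time for each dose cohort, and overall as for the primary efficacy variables". Monocyte activation is not named there and falls under the biomic measurements.

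Section 4 speaks only of mean change and its variability in the two cohorts. None of these places contains a correlation, a regression, a scatter plot or a criterion for surrogacy. The only patient-level listings planned are of adverse events and examination findings.

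**The concern.** Whether one marker can stand in for another depends on whether patients with more of the first also have more of the second, and whether the two change together in the same patient. The planned tables describe each marker on its own and discard the pairing. If the plan is followed exactly, the only evidence on the question will be whether two group means moved in the same direction after dosing. Both could fall for unrelated reasons, yet a reader told that the study would settle the question might take parallel trends as the answer. If the link is instead examined after the data are in, the many biomic markers in Section 3.2 leave wide room to choose a favourable pair.

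**Working it through.** The documents give no correlation, power or sample-size figure, so there is nothing of the plan's own to reproduce. The values of r, the 80% power and the figure of 12 usable pairs below are assumptions.

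**1. Do separate summaries determine the association?** Take 16 simulated change values with mean -8.98, SD 4.92, median -7.30, minimum -20.43 and maximum -2.76, and use the same set for both markers. Only the pairing is varied:

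| Pairing of the second marker with the first | Summaries of each marker | r |
|---|---|---|
| same order | identical | 1.00 |
| one random shuffle | identical | -0.08 |
| reverse order | identical | -0.84 |

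The tables planned in Sections 15.2 and 15.3 would be the same in all three cases. Adding the overall column does not help, because it too describes one marker at a time.

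**2. Are paired data scheduled?** PET is on Days 2 and 9 (Section 7.2.2). Research blood is daily on Days 1 to 3 (Section 6.2.2) and on Days 4 to 10 except Days 6 and 7 (Section 6.2.3). Both PET days therefore have a blood sample. The documents do not say on which days flow cytometry is run.

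**3. How precise would an added correlation be?** The Fisher interval is tanh(atanh(r) ± 1.96/√(n-3)). The critical |r| is t/√(n-2+t²), with t on n-2 degrees of freedom. Section 2 caps each cohort at 8, so n is at most 16.

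| n | Observed r | 95% CI | Critical \|r\| |
|---|---|---|---|
| 16 | 0.5 | 0.01 to 0.80 | 0.497 |
| 16 | 0.7 | 0.31 to 0.89 | 0.497 |
| 12 (assumed) | 0.7 | 0.21 to 0.91 | 0.58 |
| 8 (one cohort) | 0.7 | -0.01 to 0.94 | 0.707 |

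For n = 12: atanh(0.7) = 0.867 and 1.96/√9 = 0.653, so the limits are tanh(0.214) = 0.21 and tanh(1.521) = 0.91. The true r detectable with 80% power at n = 16 is tanh((1.96 + 0.84)/√13) = 0.65.

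**4. What does adjustment for cohort cost?** One adjustment variable replaces n-3 by n-4. At n = 16 and r = 0.5: 0.549 ± 1.96/√12 = 0.549 ± 0.566, giving -0.02 to 0.81. At n = 12 and r = 0.7: 0.867 ± 1.96/√8 = 0.867 ± 0.693, giving 0.17 to 0.92. The widening is slight, but it is enough for r = 0.5 no longer to exclude zero.

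**5. Why adjust for cohort?** Suppose two equal cohorts, no correlation within either, and both markers differing between cohorts by d within-cohort SDs. The pooled correlation is then (d²/4)/(1 + d²/4). For d = 1 this is 0.25/1.25 = 0.20. For d = 2 it is 1/2 = 0.50, about the critical value at n = 16. A dose difference alone could therefore produce an apparent patient-level link.

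**6. Why use genotype?** Section 7.2.1 classifies patients as high, mixed or low affinity binders of the ligand. Section 5.2 excludes none of these classes, and Section 15 does not use the classification. PET signal on a single day reflects affinity as well as activation, so an unadjusted Day 2 correlation across patients mixes the two.

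**The case against.** The best defence is that Section 3.2 defines the secondary outcomes as a comparison of mean changes, and the monocyte sentence then describes one of the instruments. For mean changes, Section 15.3 does supply output. The trial is also an uncontrolled descriptive pilot in which nobody would expect a formal surrogacy analysis. Part of this stands: the sentence is not the leading secondary outcome, and nothing about safety, the PET summaries or the dose comparison depends on it. But it stands under the Secondary Objectives heading, appears again in the synopsis, and promises to determine something. A correlation with its interval and a plot are themselves descriptive, so the design is no reason to omit them.

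Three stronger readings are tempting, and the documents do not support them:

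- A reader might infer that the study cannot address the question at all. It can address association, because paired samples and scans are scheduled and nothing forbids linking them. What is missing is the prespecified analysis.
- A reader might infer that summaries are planned by cohort alone. Section 15 says by cohort and overall.
- A reader might infer that adding a simple pooled correlation would settle surrogacy. It would not: dose can create such a correlation, affinity confounds the Day 2 signal, and at most 16 uncontrolled patients cannot validate a surrogate.

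**Conclusion.** The point holds in this form: the stated aim needs a patient-level association, and the planned output contains only separate summaries of each marker, so the aim cannot be answered from that output. This conclusion rests on the text of Sections 3.2, 4 and 15 and on no numerical assumption. What an added analysis could deliver is modest. Sixteen pairs is a ceiling, because Section 2 gives maximum cohort sizes, and Section 7.2.3 lets patients take part without the MRI that is used for PET co-registration. Withdrawals could also reduce the number of usable pairs. A strong within-cohort association could be seen, while a moderate one would have an interval reaching from near zero to about 0.8. The result would be exploratory whichever way it fell.

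**What to change.** 1. In Section 3.2 and the synopsis, replace the surrogate-marker wording with an exploratory aim: to assess whether peripheral monocyte activation is associated with microglial activation.

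2. Add to Section 15.3 one prespecified pairing. Name a single flow-cytometry readout and the days on which it is measured. Name a single motor-cortex [18F]FEMPA measure, since Section 7.2.2 gives none. State whether absolute or percentage change is used, since Section 15.2 lists both. For that pairing report:
   - the cohort-adjusted (within-cohort) correlation of the Day 2 to Day 9 changes, with 95% CI;
   - the Day 2 correlation, adjusted for or stratified by TSPO affinity genotype, with 95% CI;
   - a scatter plot marked by cohort and genotype.

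3. State the expected precision as a best case, with the number of usable pairs reported alongside.

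The cost is a few lines of text, one table and one plot, and a less ambitious stated aim. No visit, scan or blood draw is added, provided that flow cytometry is run on the Day 2 and Day 9 samples.

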## 4. Study Outcome

The mean rates of change and the variability around the mean of clinical, imaging and biomic outcomes in the two ALS patient cohorts will be determined over the study period. The results will inform potential future studies of the therapeutic potential of 3K3A-APC in ALS patients, and guide dosing for chronic studies.

## 5. Participants

### 5.1 Study setting and recruitment

Participants will be recruited from the ALS clinic at Macquarie University. Participants will be approached regarding the trial where possible, in routine follow up clinics. Alternatively potential participants may be approached in writing or by email by the investigators to invite them for screening.

Participants will be hospitalised at Macquarie University Hospital. PET scans and MRI scans, and lumbar punctures will be conducted at Macquarie Medical Imaging.

### 5.2 Selection of Study Population

#### 5.2.1 Inclusion Criteria

- Age 18-75 years at the time of the screening visit
- Able to provide informed consent in accordance with Good Clinical Practice (GCP), International Conference on Harmonization (ICH), and local regulations
- Willing and able to comply with scheduled visits, required study procedures and laboratory tests
- Symptom onset less than 38 months before screening
  - *Participants who fail to meet this criterion may be considered at the Principal Investigator's discretion, provided the participant is clinically stable and without any safety concerns.*
- Diagnosis of ALS less than 26 months before screening
  - *Participants who fail to meet this criterion may be considered at the Principal Investigator's discretion, provided the participant is clinically stable and without any safety concerns.*
- ALS diagnosed as definite according to the Awaji Criteria.
- Both sporadic and monogenic forms of ALS are to be included.
- Must be on a stable dose of riluzole for at least 30 days prior to the screening visit.

- Clinically definable Upper Motor Neurone signs such as increased tone, clonus, hyper-reflexia and/or extensor plantar responses
- Women may not be pregnant, lactating or planning pregnancy during the course of the study.
  - Includes a negative urine pregnancy test on day of the PET scan prior to injection ([F]FEMPA).

Women participants and female partners of participating men must be of non-childbearing potential **or** be using a highly effective method of birth control 14 days prior to until at least 24 hours after injection of [F]FEMPA.

- Non-child bearing potential is defined as a female that must be either postmenopausal (no menses for at least 12 months prior to Screening) or a female or male that is surgically sterile (bilateral tubal ligation, bilateral oophorectomy or hysterectomy, sterilization).
- Highly effective method of birth control is defined as practicing at least one of the following: A birth control method that results in a less than 1% per year failure rate when used consistently and correctly, such as oral contraceptives for at least 3 months prior to injection, an intrauterine device (IUD) for at least 2 months prior to injection, or barrier methods, e.g., diaphragm or combination condom and spermicide. Periodic abstinence (e.g. calendar, ovulation, symptothermal, post-ovulation methods) is not acceptable.

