### Schedule of Activities – ALS Subjects

Visit Number	SC	V1	V2	V3	V4	V5	V6	V7	V8	V9	V10	V11
Day of the Week		M	T	W	T	F	S	S	M	T	W	M
Visit Description (Day)	-30	1	2	3	4	5	6	7	8	9	10	15
Written Informed Consent	X											
Inclusion/Exclusion Criteria	X	X										
Vital Signs	X	X	X	X	X	X	X	X	X	X	X	X
Physical Examination	X	X							X			X
Neurological Examination	X	X							X			X
ECAS	X											
FVC	X											
ECG	X	X	X	X	X	X			X	X	X	X
Pregnancy Test (Urine)	X	X							X			
Blood Sample for TSPO genotype	X											
Clinical Laboratory Assessments	X a	X	X	X a	X a	X a	X	X	X	X	X a	X a
Research blood and urine samples	X	X	X	X	X	X			X	X	X	X
Lumbar Puncture for CSF examination				X							X	

Visit Number	SC	V1	V2	V3	V4	V5	V6	V7	V8	V9	V10	V11
Day of the Week		M	T	W	T	F	S	S	M	T	W	M
Visit Description (Day)	-30	1	2	3	4	5	6	7	8	9	10	15
MRI (ALS Protocol)			X							X		
PET imaging ([  F]FEMPA)			X							X		
Administration of 3K3A-APC - 5 doses (every 12 hours)				X	X	X						

a – Urine collected for urinalysis

Confidential

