### 6.2 Schedule of Activities

Refer to the protocol synopsis Schedule of Activities that summarizes the assessments to be conducted

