#### *6.2.2 Baseline Assessments (Day 1, 2 and 3):*

The activities for the Baseline Assessments will be completed within 30 days of completing the Screening visit. Screening and Day 1 can occur on the same day.

Baseline assessments will include the following activities and will take Day 1-3 to complete, as listed in the schedule of activities. These assessments and subsequent activities will occur as an inpatient of Macquarie University Hospital. All assessments listed below must be completed prior to enrollment of the subject into the treatment phase of the study.

- Review of continuing ability to consent
- Vital signs (blood pressure, heart rate and temperature), height and weight
- Physical examination
- ECG

- Blood collection for clinical laboratory assessments (daily)
- Urinalysis (day 3)
- Blood and urine collection for research samples (daily)
- Urine pregnancy test (Day 1)
- Neurological exam (incl. ALSFRS-R and UMN Index)
- Brain MRI (Day 2)
- Brain PET Imaging (Day 2)
- Lumbar puncture for collection of CSF (Day 3)
- Review of concomitant medications
- Review of current medical conditions
- Review of adverse events related to lumbar puncture
- Repeat review of the inclusion/exclusion criteria

Once all Visit 1 activities have been completed and the Investigator determines that all eligibility criteria have been met, the subject may be enrolled into the study. Once enrolled, the subject will be enrolled in one of two dose levels of 3K3A-APC (15mg or 30mg).

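### Section 5.2.1 requires a negative pregnancy test on the day of the PET scan, but the schedule places the baseline test on Day 1 and the scan on Day 2 (minor)

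*Combined protocol and SAP*

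**What the plan says.** The inclusion criterion on pregnancy in section 5.2.1 carries a sub-item on timing: "Includes a negative urine pregnancy test on day of the PET scan prior to injection" of [18F]FEMPA.

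The visit plan gives other days. In the Schedule of Activities the row "Pregnancy Test (Urine") is marked at screening, V1 (Day 1) and V8 (Day 8), while PET is marked at V2 (Day 2) and V9 (Day 9). The baseline list in section 6.2.2 agrees with the table: "Urine pregnancy test (Day 1") and "Brain PET Imaging (Day 2"). Section 6.2.3 puts the later test on Day 8 and the repeat scan on Day 9. Section 7.2.2 confirms that tracer is given on Day 2 and Day 9.

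Section 6.2.2 says of its Day 1 to 3 list: "All assessments listed below must be completed prior to enrollment of the subject into the treatment phase of the study". The list also contains "Repeat review of the inclusion/exclusion criteria". Its closing paragraph, however, lets the investigator enrol the participant once the Visit 1 activities are done and the criteria are judged to be met.

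**The concern.** The entry criterion asks for a test result from the scan day, and the visit plan never generates one. Staff usually work from the schedule and the visit lists, so the likeliest outcome is that the Day 1 test is done and the Day 2 test is not.

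Two things are at stake. The test is the protocol's own check before a radioactive injection, and section 12.5 accepts that imaging may carry unknown risks to an embryo or fetus. In addition, section 17 has the monitor verify that only eligible people are enrolled, so a woman tested exactly as scheduled could be recorded as failing 5.2.1. That deviation would be caused by the document, not by the site.

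**Working it through.** The plan states no figure to reproduce. The check sets the sections side by side by study day.

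| Place | Urine pregnancy test | PET scan |
|---|---|---|
| 5.2.1 | Same day as the scan, before injection | day not stated |
| Schedule of Activities | Screening, Day 1, Day 8 | Day 2, Day 9 |
| 6.2.2 | Day 1 | Day 2 |
| 6.2.3 | Day 8 | Day 9 |
| 7.1.5 | Screening, then Visits 1 and 8 (see step 2) | see step 2 |
| 7.2.2 | not covered | Day 2, Day 9 |

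1. **Lag at baseline.** Scan day minus test day = 2 − 1 = 1 day. Section 5.2.1 requires 0. Entry scans with a scheduled same-day test: 0 of 1.

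2. **Does 7.1.5 settle it?** Its visit numbers can attach to the test or to the scan. If to the test, it agrees with the schedule and the lag stays at 1 day. If to the scan, it contradicts 7.2.2 and the schedule. Neither reading yields a test on Day 2.

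3. **Lag at the repeat scan.** 9 − 8 = 1 day. This is the same gap, but 5.2.1 is an entry criterion, and by Day 9 the participant has been enrolled and treated. It is not counted as a conflict.

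4. **When is eligibility settled?** The final sentence of 6.2.2, read literally, permits the eligibility decision after Visit 1 (Day 1). A Day 2 result does not exist by then. Scheduling a Day 2 test without changing that sentence would leave 6.2.2 at odds with 5.2.1.

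5. **Tests per woman of childbearing potential.**
 - Now: screening, Day 1, Day 8 = 3.
 - Move V1 to V2: screening, Day 2, Day 8 = 3 (3 − 3 = 0 extra), baseline lag 2 − 2 = 0.
 - Add V2 and keep V1: screening, Day 1, Day 2, Day 8 = 4 (4 − 3 = 1 extra), baseline lag 0.
 - Optional move of V8 to V9: no extra test in either case, repeat lag 9 − 9 = 0.

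6. **Is moving V1 acceptable?** Without a Day 1 test, the latest result at the Day 1 eligibility check is the screening one. Its age can be 0 days, because 6.2.2 allows screening and Day 1 to coincide. At the other end, 6.2.2 says "The activities for the Baseline Assessments will be completed within 30 days of completing the Screening visit". With Day 3 at the limit, Day 1 falls at 30 − 2 = 28 days. The schedule's screening column of Day −30 gives 30 days without a Day 0, or 31 with one. The range is therefore 0 to about 31 days. No exposure follows from an old result: tracer is first given on Day 2, after the moved test, and study drug on Day 3.

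**The case against.** The best case for leaving the text alone is that nothing stops a site from complying. Section 5.2.1 states the requirement in full, and section 6.2 refers only to a "Schedule of Activities that summarizes the assessments to be conducted", so the table need not be exhaustive. Section 6.2.2 lists a repeat eligibility review, and a urine test on an existing inpatient day is trivial. A site that follows only the schedule still has a result from the day before, in an inpatient who must use contraception from 14 days before until at least 24 hours after injection. The companion protocol (12.4) and the Operation Manuals (13.1), which I have not seen, may contain a same-day prompt.

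Most of this stands, and it limits the point to a minor one. It does not remove the mismatch. The visit list in 6.2.2, and not only the summary table, gives Day 1. Section 13.1 leaves to the manuals what the protocol does not describe, and this test is described here with a day.

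Three stronger readings are tempting, and the documents do not support them:

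- A reader might infer that the criterion cannot be met. It can: one unscheduled test on Day 2 satisfies both texts.
- A reader might infer that the Day 9 scan breaches 5.2.1 as well. That section does not clearly govern the second injection.
- A reader might infer that the Day 1 test must be kept whatever else changes. Neither tracer nor study drug is given on Day 1, and the Day 2 test would precede both, so moving it is a sound option.

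**Conclusion.** The conflict at baseline is real in the current text: the same-day test that 5.2.1 requires is absent from the schedule and from 6.2.2, by one day. A site following the schedule alone would not meet the criterion for a woman of childbearing potential.

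The point is minor. Absolute risk is small, and no endpoint, dose or analysis is affected. Planned enrolment is 16, and the number of women of childbearing potential is not given; it could be anywhere from 0 to 16, so the counts above are per woman. I assume that the test in 5.2.1 is meant for women of childbearing potential, as section 6.2.1 says of the screening test. The mismatch between sections is certain. Whether any test would be missed in practice is not, because it depends on site habits and on manuals I have not seen.

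**What to change.** Schedule the urine test at V2 (Day 2), with the result read before tracer injection, in both the Schedule of Activities and 6.2.2. Either move the V1 test there or keep V1 and add one test. Then:

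- Reword 7.1.5 so that the visit numbers plainly refer to the test and match the new schedule.
- Amend the closing sentence of 6.2.2 so that eligibility is confirmed only after the Day 2 result, not on completion of the Visit 1 activities.
- Optionally, move the V8 test to V9 (Schedule of Activities, 6.2.3 and 7.1.5), so that the second injection has the same check. No tracer or study drug is given on Day 8.

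If the sponsor considers a day-before test sufficient, rewording 5.2.1 to say so also removes the conflict at no cost in tests, but it relaxes the stated safeguard.

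The cost is 0 extra urine tests per woman if V1 is moved, or 1 if a test is added. The optional V9 move adds none. No new visit is needed, because Days 2 and 9 are already inpatient days. The edits are short, but under section 13.3 they need Steering Committee and ethics committee approval as a protocol amendment.
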